Patients ≥ 8 years of age are to be approached for assent if the patient is extubated, no longer under the influence of sedatives and analgesics, and the patient is actively receiving early or late parenteral nutrition per study. If no assent obtained because the patient is sedated and unable to participate in the assent process, document this on the assent form and keep in patient study file. If the child does not provide assent once able to cooperate with assent, the intervention is discontinued at that point. All data obtained prior to assent will be utilized. File original assent forms with original parental

consent form in the patient study file and document assent on the SUPPER Enrollment form. Make two copies of the assent form, one for the family and one for bedside.

Randomization

Randomization takes place within 48 hours of PICU admission or initiation of mechanical ventilation. Patients are blocked randomized by age and pre-existing acute or chronic malnutrition (based on admission weight for age BMI z score) to either early or late parenteral nutrition (PN) supplementation. There are 9 randomization stratifications (see table below). Randomization cards are pre-generated; random sequence was created using a random generator with atmospheric noise at random.org. BMI z-score is derived from one of two websites. If <2 years of age, use www.emmes.cpm/study/ped/resources/htwtcalc.htm; if ≥2 years of age, use www.stokes.chop.edu/web/zscore/index/php.

	1month to <3 years	3-10 years of age	11-16 years of age
BMI z score < -1 and >-2 (Low)	A1	B1	C1
BMI z score -1 to +1 (Normal)	A2	B2	C2
BMI z score > +1 and < +2 (High)	A3	B3	C3

To randomize a successfully consented patient, use age and BMI z score to determine which randomization block the patient should be in. Choose the first randomization envelope in the pack. The envelope will have a card stating the intervention arm. Record the patient's study ID, patient age, BMI z-score, name of study personnel randomizing, and date/time of randomization on the card, and staple to the SUPPER Screening Form. Document date, time and study intervention randomized on the patient's SUPPER Screening form and SUPPER Enrollment Log.

Once randomized, email the study PI the patient's study ID, age BMI z score, date and time of randomization, and assigned intervention.

Patient Kits and Supplies

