Each successfully enrolled and randomized patient will have a patient study file. This file will contain all forms for that patient. SUPPER Study Sample Kits have been provided for the collection of blood, and stool for this study. One kit is to be used per patient.

Early Parenteral Nutrition Supplementation (EPN)

Supplies, Medications, and Forms to have on hand when starting:

SUPPER Tablet with SUPPER Titration

Supplemental PN (Baxter Clinimix for patients 1 year of age and older; in-house custom PN for infants 1 month and <1 year)

SUPPER Patient Study Binder

SUPPER Sample Kit

Tape measure to perform mid upper arm circumference

Once randomized to Early Parenteral Nutrition (EPN), patients are to be started on the PN intervention within 2 hours of randomization. Patients randomized to EPN will receive enteral nutrition with supplemental PN for 168 hours. Calorie goal and titration of PN/IL are according to the SUPPER Titration Tool. **If at any point the clinical team feels that it is unsafe to continue PN, discontinue PN immediately and record this as a protocol violation. Ensure appropriate monitoring of blood glucose after abrupt discontinuation of PN.** Reducing the hourly rate of PN to achieve clinically indicated fluid restriction is also acceptable for the study protocol. All attempts should be made, and the study protocol is designed to avoid fluid overload as a result of PN. The SUPPER Titration Tool does not allow PN to exceed MIVF rates. Obtain mid upper arm circumference.

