Prior to EPN Hour 0, set up SUPPER Tablet at bedside. Open the SUPPER Titration and enter all of the patient demographics, formula, TPN, and fluid information at the top. Calculate Schofield 100% BMR (height/weight). Rates for EN, PN, Lipids, and remaining available hourly fluids will populate. Print SUPPER Titration for bedside and study binder and review with the bedside nurse. A new SUPPER Titration Tool will need to be created for any change in formula kcal content, calorie goal, or new total fluid order (such as in the case of fluid restriction). As EN feeds are advanced, PN and Lipids decrease. If EN is held or reduced, titrate PN and Lipids according to SUPPER Titration sheet. Choice of PN is based on patient age. If the patient is 1 year of age or older, patients will receive Baxter Clinimix. Patients between 1 month of age and <1 year of age will receive in-house custom PN. The early EN guideline in place for clinical use at CHOP will be used to increase enteral feeds. The goal should be to reach full enteral feeds within 48 hours of initiating EN.

The SUPPER Algorithm uses Schofield's equation to calculate the initial kcal/day goal. Patients are to initially receive a max of 75% of calorie goal and 1.5 gm/kg/day protein for the first 24 hours. Patients will receive 100-120% of MREE (or 100-120% of Schofield predicted BMR in the setting of no MREE) and 2-3gm/kg/day protein with combined PN and EN by study day 2, not to exceed 1600mL/M²/day in fluids (See Table at end of MOO). If there is >20% discrepancy between the unit dietician's usual practice for determination of kcals/day for a given patient and the Schofield predicted BMR, please call the U of A PI to discuss altering the individual patient's kcal goal during the 7-day study intervention. The bedside nurse will titrate PN to maintain calorie goal and protein every 4 hours with the aid of the SUPPER Titration Sheet in place of usual total IVF orders. As patient tolerates increased EN, PN and IL are decreased. In this manner, in the Early PN arm, the patient's delivered calories and protein remain constant, although the route of delivery changes as enteral feeds advance.

	0 Hour	12 Hour	24 Hour	48 Hour	72 Hour	96 Hour	120 Hour	144 Hour	168 Hour
Blood Sample 2mLs	X	X	X	X	X	X	X	X	X
Fecal Samples (if patient has stool)	X		X	X	X	X	X	X	X
Metabolic Cart (REE)	Occurs Between 0 hour and 48 hours (DCMC Only)					Occurs Between 96 hours and 144 hours (DCMC Only)			

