To assess 28 Day Vitals first check to see if the patient is still hospitalized or if the patient died while hospitalized. If patient is not hospitalized, use the SUPPER Contact form to contact the patient's parents/guardians. Three attempts should be made to contact the parents/guardians. If the third attempt is unsuccessful, attempt to contact the patient's primary care physician. If the patient has not

been seen by the primary care physician since hospitalization, assess vital status from county death records. If you can successful contact either the patient's parents/guardians or primary care physician obtain information on whether the patient's condition is better, the same, or worse from condition at discharge. Also obtain information on whether the patient was readmitted to the hospital on or before 28 Days.

Late Parenteral Nutrition Supplementation (LPN)

Supplies and forms for have on hand after randomization.

SUPPER Tablet with SUPPER Titration

SUPPER Patient Study Binder

SUPPER Sample Kit

Tape measure to measure mid upper arm circumference

Once randomized to Late Parenteral Nutrition (LPN), patients are to be started on EN within 2 hours of randomization if not already started. Patients randomized to LPN will receive enteral nutrition for 168 hours and supplemental PN if not reaching 80% goal feeds starting at Hour 96 for a total of 72 hours. Calorie goal and titration of feeds are according to the SUPPER Titration. Obtain mid upper arm circumference.

Prior to LPN Hour 0, set up SUPPER Tablet at bedside. Open the SUPPER Titration and enter all of the patient demographics, formula, and fluid information at the top. Rates for EN and remaining fluids will populate. Print SUPPER Titration for bedside and study binder and review with the bedside nurse.

The SUPPER Titration uses Schofield's equation to calculate the initial kcal/day goal. Patients are to initially receive a max of 75% of calorie goal and 1.5gm/kg/day protein for the first 24 hours. Patients will receive 100-120% of MREE and 2-3gm/kg/day protein with combined EN by study day 2, not to exceed 1600mL/M²/day in fluids. As the patient can tolerate, EN is to be escalated every 4 hours to full kcal/day goal.

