- Provide input to the investigators on the progress of the study, including periodic assessments of the data quality and timeliness, participant recruitment, accrual and retention, participant risk vs benefit, performance of the study sites, and other factors that may affect study outcomes;
- Review areas of concern regarding the performance of individual sites and provide comment to the investigators on actions to be considered regarding sites that perform unsatisfactorily;
- Consider factors external to the study when relevant information becomes available, such as scientific or therapeutic developments that may have an impact on the safety of the participants or the ethics of the study;
- Provide input to the investigators on modification of the study protocol or possible early termination of the study because of attainment of study objectives, safety concerns, low likelihood of showing a benefit of the intervention, or inadequate performance (such as enrollment and retention problems);
- If appropriate, review the interim analysis of efficacy in accordance with stopping rules which are clearly defined in the protocol and have the concurrence of the DSMB;

Statistical Analysis Plan:

Aim 1. We will assess differences between cumulative percent of goal energy and protein by study arm. We will report means and standard deviations as standard descriptive statistics. We will compare means between study arms with the Student's t tests as we expect cumulative percent of goal energy and protein to have normal distributions. Results will be considered significant at $p < 0.05$. Relationships between cumulative energy and protein delivered with clinical characteristics, mid upper arm circumference changes, and weight for age z scores will be reported by Pearson's correlation coefficient.

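### Aim 1 names Student's t test on normality grounds alone, although the design makes unequal spread plausible; naming Welch's test in advance is a minor, nearly free improvement

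*Combined protocol and SAP*

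**What the plan says.** - **Test.** Statistical Analysis Plan, Aim 1: "We will compare means between study arms with the Student's t tests". The reason given in the same sentence is that "we expect cumulative percent of goal energy and protein to have normal distributions". The significance level is 0.05. Equal variance, an unequal-variance version and a fallback are not mentioned there or elsewhere.
- **Early arm.** The EPN section has the bedside nurse adjust PN every 4 hours, so that "in the Early PN arm, the patient's delivered calories and protein remain constant". The same section leaves room for variation: "Reducing the hourly rate of PN to achieve clinically indicated fluid restriction is also acceptable for the study protocol". PN may also be stopped if judged unsafe, and it may not exceed the maintenance fluid rate.
- **Late arm.** The LPN section relies on EN alone at first: "As the patient can tolerate, EN is to be escalated every 4 hours to full kcal/day goal". Under Initiation of PN at Hour 96, PN is added only for a child below 80% of the calorie goal, and is then titrated to goal.
- **Allocation.** The Randomization section uses blocked randomization in nine age-by-BMI strata. It states neither block size nor allocation ratio.
- **Size.** The figure of 40 subjects comes from the Aim 2 paragraph of the SAP. The documents give no sample size calculation, and no SD, for Aim 1.

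**The concern.** The outcome is the very quantity that the early arm is titrated to control. If the intervention works as described, it should narrow that arm's distribution as well as raise its mean. For the first 96 of 168 hours the late arm has no PN to offset differences in EN tolerance. The plan therefore argues one assumption of its test (normality) and is silent on the one that its own intervention is more likely to disturb.

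At stake are the p value and any confidence interval for the only between-arm test in Aim 1. If the more variable arm, presumably the late one, is the smaller, the pooled standard error is too small and the result looks too certain. If that arm is the larger, the result is too cautious.

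**Working it through.** **Inputs from the documents:** Student's t test, level 0.05, 40 children, nine strata.

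**Assumptions:** two-sided test, 1:1 allocation, normal data, late:early SD ratio r from 1 to 4, block sizes 2 to 8, equally likely strata.

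**1. The plan's own level.** With equal SDs (r = 1), the pooled test gives 5.0% at every split tried. The nominal level is reproduced, and unequal arm sizes alone do no harm.

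**2. Why both conditions are needed.** Set the early SD to 1 and the late SD to r.

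- True variance of the difference in means: 1/n_E + r²/n_L
- Expected pooled estimate: [(n_E − 1) + (n_L − 1)r²]/(N − 2) × (1/n_E + 1/n_L)

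For r = 2:

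- 22 early/18 late: true 1/22 + 4/18 = 0.268. Pooled (21 + 68)/38 × 0.1010 = 0.237. Ratio 0.88, so the standard error is about 6% too small.
- 18/22: true 1/18 + 4/22 = 0.237. Pooled (17 + 84)/38 × 0.1010 = 0.268. Ratio 1.13, so the standard error is about 6% too large.
- 20/20: both equal 0.250.

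**3. Type I error of the pooled test at N = 40**, by numerical integration over the two sample variances:

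| Early/late | r = 1 | r = 1.5 | r = 2 | r = 3 | r = 4 |
|---|---|---|---|---|---|
| 20/20 | 5.0% | 5.1% | 5.2% | 5.4% | 5.5% |
| 21/19 | 5.0% | 5.5% | 6.0% | 6.5% | 6.7% |
| 22/18 | 5.0% | 6.0% | 6.8% | 7.6% | 8.0% |
| 24/16 | 5.0% | 7.0% | 8.5% | 10.2% | 10.9% |
| 19/21 | 5.0% | 4.7% | 4.6% | 4.5% | 4.5% |
| 18/22 | 5.0% | 4.3% | 4.0% | 3.7% | 3.7% |
| 16/24 | 5.0% | 3.5% | 2.9% | 2.4% | 2.3% |

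Simulation agrees to about 0.1 percentage points: over r = 1.5 to 4 it gives 5.0 to 5.5% at 20/20, 6.1 to 8.0% at 22/18 and 3.7 to 4.2% at 18/22. Welch's test lies between 4.9% and 5.1% in every cell of the table.

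**4. How often the arms would be unequal.** With blocks of 4, a split of 22/18 or worse in either direction occurs in about 26% of simulated trials. The early arm reaches 22 or more in about 13% and 23 or more in about 3%. Across block sizes 2 to 8, the chance of 22/18 or worse in either direction runs from 14% to 45%, and of 24/16 or worse from 0% to 8%.

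**5. Averaged over the allocation (blocks of 4).** The pooled test's error is about 5.1%, 5.3%, 5.5% and 5.7% for r = 1.5, 2, 3 and 4.

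**6. Price of Welch when the SDs are equal.** For a true difference of 0.9 SD, power is 79.2% (Student) against 79.1% (Welch) at 20/20, and 77.6% against 77.2% at 24/16.

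**The case against.** The strongest reply is that the problem may be very small. No SD is given, and both arms have features that bring their spreads closer together. Early-arm PN can be reduced or stopped and total fluid is capped. Both arms share the same reduced calorie ceiling in the first 24 hours. Late-arm children below 80% of goal at hour 96 receive PN titrated to goal. Averaged over likely allocations, the error is below 6%. The design feature that suggests unequal variances also makes a real difference in means likely, so a small shift in error under equal means would seldom change the conclusion. This is a pilot, and the SAP already reports SDs by arm, so unequal spread would be visible. The total of 40 is itself uncertain for Aim 1: Interim Safety Analysis places a safety look after 40 are enrolled and refers to stopping before enrolment is complete. In a larger trial the same absolute imbalance would matter less.

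Most of this stands, and it limits the size of the point. Two things remain. Interval coverage is 100% minus the type I error whatever the true difference, so at 22/18 a pooled 95% interval would cover about 92 to 94%. And seeing unequal SDs afterwards is a poor time to change the test, since the Data and Safety Monitoring Plan says the investigative team knows group assignment.

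Stronger readings that a reader might infer, and why the documents do not support them:

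- *The error rate is wrong whenever the arms differ in size.* With equal SDs the pooled test is exact at any split.
- *The protocol establishes that the variances are unequal.* It makes this plausible; it states no SD and does not exclude equal ones.
- *There is a 26% chance of an inflated error.* That figure counts both directions; in about half of those trials the late arm is the larger and the test is conservative.
- *Separate envelope packs per site make imbalance likelier still.* The Randomization section does not say that packs are separate by site.
- *The normality expectation is mistaken.* Nothing here tests it; all the calculations assume it.

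**Conclusion.** The point holds as a minor one. The plan commits to Student's t test without addressing equal variances, in a design that gives good reason to expect less spread in the early arm. Under the stated assumptions, the pooled test's error would be about 6 to 8% at 22/18 and about 4% at 18/22, and close to 5% with equal arms. The expected distortion is modest and its direction cannot be known in advance. It becomes material only at about 24/16 or worse, for example after uneven withdrawals. The result rests on an SD ratio inferred from the design rather than stated, on 1:1 allocation with an assumed block size, and on 40 children in the analysis. It is not a gross error.

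**What to change.** In the Aim 1 paragraph of the SAP, replace Student's t test with Welch's unequal-variance t test for both energy and protein, and state that the difference in means will be reported with its Welch 95% confidence interval. Make the change before outcome data are seen. It needs a one-line edit, no extra data and no change to the conduct of the trial. If the SDs turn out equal, the loss of power is under 0.5 percentage points. If they do not, the test holds about 5% at every split and ratio examined.

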Before initiation of EPN, collect 0 hour blood sample. This may be collected within 4 hours prior to beginning EPN to coordinate with clinical laboratory sample collection. Continue with timed sample collections as shown in the table above, using the time of EPN initiation as the starting point. All samples may be collected \pm 2 hours from target time. If patient has continuous vasoactive infusions and the infusion has been titrated within the last hour of the time of sample collection, wait at least 1 hour from time of last vasoactive infusion change. (For example, sample collection is to be drawn at 8:00am, and vasoactive infusion was titrated last at 7:30am, wait until 8:30am for sample collection). Where ever possible, match sample collection with clinical labs to reduce line access and risk of infection. For clinical variables recorded on the sample collection log use clinical data obtained within the hour prior to sample collection. (i.e. if sample collection is at 0805, record CVP from the clinical record between 0705-0805.)

While writing initial orders for EN/PN, also include orders for PINI. This includes albumin, c-reactive protein, fibrinogen, transferrin, and prealbumin. If these values are not already available pre-randomization, then obtain within 4 hours of randomization.

If the care team decides the patient does not require artificial nutrition and/or central access lines are no longer needed, PN regimen is to be discontinued.

After Initiation of EPN:

SUPPER Pre-Admit Questionnaire and SUPPER Baseline Form

Once the patient has been initiated on EPN, retrieve the SUPPER Pre-Admit Questionnaire from the patient study file. SUPPER Pre-Admit Questionnaire should be completed within 24 hours of randomization. Ideally, study personnel should sit with family and complete the questionnaire to assist the family with any questions and ensure that questionnaire is successfully completed.

Using the patient's medical record, complete the SUPPER Baseline Form. Include only information prior to time of randomization. For variables with multiple values, choose that which is closest to randomization.

SUPPER Daily Data Collection and SUPPER EN/PN Tracking Log

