The LPN intervention starts with the initiation of enteral feeds. Initiation of EN should take place within 2 hours of randomization if the patient was not already on EN. Within 2 hours of randomization, collect 0 hour blood sample and continue with timed sample collections as shown in the table below using the time of LPN initiation as the starting point. All samples may be collected \pm 2 hours from target time. Where ever possible, match sample collection with clinical labs to reduce line access and risk of infection.

While writing initial orders for EN also document PINI. This includes albumin, C - reactive protein, fibrinogen, transferrin, and prealbumin. If these values are not already available pre-randomization, then obtain within 4 hours of randomization.

	0 Hour	12 Hour	24 Hour	48 Hour	72 Hour	96 Hour	120 Hour	144 Hour	168 Hour
Blood Sample 2mLs	X	X	X	X	X	X	X	X	X
Fecal Samples (if patient has stool)	X		X	X	X	X	X	X	X
Metabolic Cart (REE)	Occurs Between 0 hour and 48 hours (DCMC Only)					Occurs Between 96 hours and 144 hours (DCMC Only)			

SUPPER Pre-Admit Questionnaire and SUPPER Baseline Form

Once LPN is initiated and 0 hour sample is collected, retrieve the SUPPER Pre-Admit Questionnaire from the patient study file. SUPPER Pre-Admit Questionnaire should be completed within 24 hours of randomization. Ideally, study personnel should sit with family and complete the questionnaire to assist the family with any questions and ensure that questionnaire is successfully completed.

Using the patient's medical record, complete the SUPPER Baseline Form. Include only information prior to time of randomization. For variables with multiple values, choose that which is closest to randomization.

SUPPER Daily Data Collection and SUPPER EN/PN Tracking Log

SUPPER Daily Data Collection forms are provided for each of the intervention days and can be found in the patient's study file. For variables with multiple values use value closest to 8:00am, unless otherwise noted. For Day 0 Daily Data Collection, only use post randomization information. These forms do not need to be completed in real time if normal bedside charting clearly provides required information, but we recommend completing them the day after they occur (ex: Day 0 completed on Day 1).

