Aim 2. We will assess differences between FABP2, claudin 3, citrulline, lactulose/mannitol ratios, and by study arm. Descriptive plots: serum biomarker (y-variable) over time (x-variable) will be fit, with linear and smoothing splines. Plots are qualitative. Splines allow examination of possible nonlinear relationships and can be used to specify nonlinear or change-point models. We utilize one-way repeated measures ANOVA with the intestinal barrier assays as continuously measured outcomes and time (1,2,3,5, and 7 days) as explanatory variables. If the slope of the serum biomarkers is linear, then change in the slope over time will be calculated using a linear mixed effects model with an AR(1) variance-covariance structure. The variance-covariance structure allows for measurements taken closer together to be more similar than those farther apart in time, and adjusts the standard errors for this correlation. If the relationship between the serum biomarker is not linear in time, then change-point or nonlinear mixed effects models will be used. Aim Multivariable regression analysis will evaluate possible effect modification, or mediation, for non-invasive measures of intestinal epithelial barrier function. Effect modifiers are the interactions with PN group; mediators are those variables that could have a potential additive effect with the PN group. Additionally we will assess any potential confounding that might be present by assessing the change in the parameter estimate for the PN group effect. Potential modifiers, mediators, and confounders, include clinical variables, center effects, and severity of illness. We will test associations between measures of intestinal function and clinical variables, severity of illness, as well as dose and route of nutrition. With 40 subjects total, we will be able to include up to 4 possible predictors; therefore, if effect modifiers are warranted, model simplification will be necessary. If the study is stopped early the analysis plan may be modified due to small sample size.

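### For the plasma barrier markers, the Aim 2 plan specifies no use of the hour-0 sample scheduled in both arms, so the arm comparison gives up precision at about 40 subjects

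*Combined protocol and SAP*

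**What the plan says.** Aim 2a is the effect of early combined EN and PN on intestinal barrier function. In the Statistical Analysis Plan, Aim 2 opens with "We will assess differences between FABP2, claudin 3, citrulline, lactulose/mannitol ratios, and by study arm". The first named analysis is a one-way repeated measures ANOVA with "intestinal barrier assays as continuously measured outcomes and time (1,2,3,5, and 7 days) as explanatory variables". If the trend is linear, "change in the slope over time will be calculated using a linear mixed effects model with an AR(1) variance-covariance structure"; if not, change-point or nonlinear mixed models are used. The time points for the mixed models are not restated. Arm appears in the opening sentence and again as the PN group effect in the multivariable regression; the ANOVA names no arm term.

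On covariates, the plan says: "Potential modifiers, mediators, and confounders, include clinical variables, center effects, and severity of illness". It adds: "With 40 subjects total, we will be able to include up to 4 possible predictors". No baseline marker value, change from baseline or common-baseline model is mentioned.

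The sampling tables for both arms schedule a 2 mL blood sample at hour 0. In the EPN section: "Before initiation of EPN, collect 0 hour blood sample". In the LPN section: "Within 2 hours of randomization, collect 0 hour blood sample". Study PN in the late arm cannot begin before hour 96.

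**The concern.** Each child is scheduled to have a plasma value before study PN, but no planned analysis is said to use it. Children range from 1 month to 16 years. Randomization is stratified by age band and BMI z-score, not by marker level or illness severity. Between-child differences present at entry will therefore add to the spread of the follow-up values in each arm.

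With 20 per arm, chance alone gives a standard error of sqrt(2/20) = 0.32 SD for the arm difference at hour 0. Whatever part of such a difference persists stays in an unadjusted comparison of levels. At stake is the precision of the Aim 2a estimate, and also prespecification: without a stated rule, the choice between adjusted and unadjusted results could be made after the data are seen.

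**Working it through.** **The plan's own figure.** The Aim 2 text gives 40 subjects and at most 4 predictors. It gives no effect size, SD, power or correlation, so the 40 cannot be reproduced. The ratio 40/4 = 10 subjects per predictor is consistent with a common rule, but the plan does not state one.

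**Inputs.** From the documents: 40 subjects, follow-up days 1, 2, 3, 5 and 7, hour 0 scheduled in both arms, and AR(1) named for the mixed model. Assumed: 1:1 allocation (20 per arm), complete data, equal variance over time, the three markers assayed in the scheduled blood, and the correlation itself. AR(1) is taken on elapsed days, so the correlation between times s and t is r^|s−t|. Compound symmetry (constant correlation r) is shown as the contrast.

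**Mean of the five days.** Let v be the variance of one child's five-day mean and g its covariance with the hour-0 value, in units of the marker's variance. The arm difference has variance 2v/20 without hour 0 and 2(v − g²)/20 with it. The proportional cut is g²/v.

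- Worked case, AR(1) with r = 0.5. The ten pairs of days have lags 1 (twice), 2 (three times), 3 (once), 4 (twice), 5 (once) and 6 (once). Their correlations sum to 2.047, so v = (5 + 2 × 2.047)/25 = 0.364. Then g = (0.5 + 0.25 + 0.125 + 0.031 + 0.008)/5 = 0.183, and the cut is 0.183²/0.364 = 9%.
- Compound symmetry: v = (1 + 4r)/5 and g = r, so the cut is 5r²/(1 + 4r). At r = 0.5 this is 1.25/3 = 42%; at r = 0.7 it is 2.45/3.8 = 64%.

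| Structure | r | v | g | Variance cut | SE of arm difference, without → with hour 0 (SD units) |
|---|---|---|---|---|---|
| AR(1) | 0.5 | 0.364 | 0.183 | 9% | 0.191 → 0.182 |
| AR(1) | 0.7 | 0.518 | 0.357 | 24.5% | 0.228 → 0.198 |
| AR(1) | 0.9 | 0.791 | 0.702 | 62% | 0.281 → 0.173 |
| Compound symmetry | 0.5 | 0.600 | 0.500 | 42% | 0.245 → 0.187 |
| Compound symmetry | 0.7 | 0.760 | 0.700 | 64% | 0.276 → 0.164 |

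**Single days.** The cut on day t under AR(1) is r^(2t). At r = 0.7 it is 49% on day 1, 24% on day 2, 12% on day 3, 3% on day 5 and 0.7% on day 7. At r = 0.5 it is 25% on day 1 and under 2% from day 3.

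**Arm difference in slope.** Generalized least squares variances were compared with a model on days 1, 2, 3, 5 and 7 only, for r from 0.3 to 0.9 under both structures:

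- hour 0 entered as a main-effect covariate: ratio 1.000, so no gain;
- hour 0 added as a further outcome with arm-specific intercepts: ratios 0.682 to 0.818, a cut of about 18–32%;
- hour 0 as an outcome with a common mean and a linear arm effect starting there: ratios 0.264 to 0.663, a cut of about 34–74%. Part of this comes from the assumption that the arm effect is linear from hour 0.

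**The case against.** Five points can be made for the plan.

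1. *Power.* A reader might infer a headline power gain. In a two-sample t test on one follow-up value with 20 per arm, baseline correlation 0.5 would lift 80% power to about 90%. The documents do not support quoting this: the t test is specified for Aim 1 only, Aim 2 has no power target, and under AR(1) no single correlation applies to all follow-up days.

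2. *Slope.* The mixed model targets change over time, and adding hour 0 as an ordinary covariate does nothing for the arm difference in slope. This stands and determines the form of the fix.

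3. *Exclusion.* A reader might infer that the plan rules hour 0 out. It does not go that far. The mixed models do not restate their time points, and the list of potential confounders is open-ended. Day numbering is also unclear. The daily forms use a Day 0, which puts hour 0 outside the listed days. The feeding text limits intake for the first 24 hours and then sets a goal for study day 2, which suggests that day 1 starts at hour 0. On that count hour 0 is already an outcome, and for the slope only the common-mean constraint remains to be gained: 1 − 0.297/0.722 = 59% under AR(1) at 0.5, but 1 − 0.617/0.682 = 10% under compound symmetry at 0.7.

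4. *Bias.* A reader might infer that chance imbalance makes the comparison invalid. It does not: the unadjusted randomized comparison is unbiased, only less precise.

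5. *Scope.* The opening sentence also covers lactulose/mannitol. That test is in neither sampling table, and its omission is not a violation at one site. In the late arm, the hour-0 sample may follow the start of enteral feeds. Both limits stand.

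**Conclusion.** The point holds as a gap in specification for FABP2, claudin 3 and citrulline. Both arms schedule an hour-0 value before study PN, though not necessarily before enteral feeding, and the Aim 2 plan does not say how it enters the arm comparison.

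The loss depends on a correlation that the documents do not give. For the average level it ranges from modest (9%) to large (62–64%) over the values shown; for day 7 alone it can be negligible. For the slope it depends on how hour 0 enters the model. The standard errors assume 20 per arm. The Interim Safety Analysis also uses 40 as its trigger, so final enrolment may be larger, but the proportional cuts do not depend on the number of children. This should be changed; it does not invalidate the planned comparison.

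**What to change.** For each of the three plasma markers, specify one mixed model with hour 0 as a response (log scale if skewed), its mean constrained equal across arms, and time and arm-by-time terms for the later samples. Report the resulting baseline-adjusted arm difference as the Aim 2a estimate. State which sampling hours correspond to days 1, 2, 3, 5 and 7. This model also supplies the arm term that the one-way ANOVA lacks and keeps children who have no hour-0 sample.

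The common mean requires that allocation has not yet affected the hour-0 value. Record the draw time relative to the start of enteral feeding, and add a sensitivity analysis without hour-0 values drawn after feeds were started following randomization.

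If hour 0 is instead entered as a covariate in the multivariable regression, count it within the four-predictor limit: 4 − PN group − hour 0 leaves two slots.

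The cost is a few sentences in the SAP. No new visit or blood draw is needed.
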